#### • Congratulations! How did the birth go?

*Listen attentively as she shares her birth story, asking open-ended questions as appropriate. Examples:* 

- How did breastfeeding go in the hospital?
- Let's review your short term breastfeeding goals. Read through her goals together.
- In what ways were the hospital staff and your support persons supportive of your breastfeeding goals?
- How is breastfeeding going so far?
- Do you have any concerns or questions?
- Based on mother's responses, review Breastfeeding Support Topics as needed:
  - 1. Latch and positioning
  - 2. Feeding cues and normal infant feeding patterns
  - 3. Emotional challenges
  - 4. Breast and nipple care
  - 5. How to know baby is getting enough breast milk (diapers, weight gain over time)
- Let's take a few minutes to review your long term breastfeeding goals.
  - Read through her goals together.
  - Provide reinforcement of exclusive breastfeeding benefits and recommended duration (the first 6 months). As we discussed at our first visit, breastfeeding exclusively for the first 6 months provides many benefits to both you and your baby. List and discuss benefits. Remind mother that exclusive breastfeeding is only feeding baby breastmilk, either at the breast or pumped and given in a

bottle. No water, juice, cow's milk, formula, or solids like baby cereal or baby food.

- One of those benefits is weight loss, because your body is using extra calories to make milk. If you breastfeed exclusively for the first 6 months, that is equivalent to 90,000 calories! That's equal to over 650 scoops of ice cream!
- Provide participant with the reminder to utilize the Coffective app as needed.
- From initial weight management and healthy lifestyle goals established with participant you may provide relevant educational materials which can be obtained from:
  - o USDA- Choose MyPlate
    - https://www.choosemyplate.gov/ten-tips
  - Exercise Guide for Post-partum mothers
    - http://makeyourbodywork.com/postpartum-exercise-guide/
- Our next home visit will be when your baby is 6 weeks old, around the time of your 6 week postpartum check up with your doctor/midwife. Let's plan a date and time.
- Keep in mind that additional home visits can be done as needed if you request them. If you're having problems or unsure of something, just ask! I'm here to help you. I will be calling you monthly, but if questions arise before my call or visit, please feel free to contact me. After breastfeeding has been established, Mama Bear Peer Counselors will make monthly calls and continue to track in RedCap.
  - In those calls, follow up on usage of weight management application and Healthy Lifestyle goals set.
- At 6 week visit, discuss the use of a scale. Instruct mother not to use it daily, because inches are lost before pounds.

### Reminders

- MBPCs will call [name], CLS after their first couple of postnatal home visits to discuss any questions they could not answer and/or to debrief about the entire visit.
- MBPCs will also have access to a contracted Lactation Consultant to assist with any breastfeeding challenges they cannot resolve.
- MBPCs have a "Yield List" that indicates when they Yield to a Lactation Expert or Health Care Provider.

#### **Educational Materials and Resources available for visits**

#### **Prenatal Breastfeeding Education**

Coffective Checklist Coffective Counseling sheets Breastfeeding Matters fact sheets Express Yourself fact sheet Making Milk-Yes You can fact sheet Feeding Your New Baby-Eating Smart-Being Active

#### **Postpartum Breastfeeding Education**

Getting Milk from Mom to Baby fact sheet Making it Work fact sheet Diaper Diary

Healthy Lifestyle Prenatal/Post-Partum

- https://www.womenshealth.gov/breastfeeding/index.html?from=AtoZ
- https://www.womenshealth.gov/itsonlynatural/
- https://www.womenshealth.gov/files/assets/docs/breastfeeding/itsonlynatural/brea stfeedingguide-africanamerican-english.pdf USDA- Choose MyPlate
- https://www.choosemyplate.gov/ten-tips Exercise Guide for Post-partum mothers
- http://makeyourbodywork.com/postpartum-exercise-guide/ Postpartum Birth Control Education

one as header

#### **Interventionist Protocol**

#### **Contact and Scheduling**

- In REDCap view the "Record Status Dashboard" to identify participants who are approaching the point of scheduling either a (Prenatal visit, Early Postpartum Visit, or 6 Week Postpartum Visit). Visit Reports can be drafted that will project the "scheduled date" for the participant's home/clinic visit to be completed. Upon either monitoring or receipt of those reports, visits should be scheduled immediately.
- 2. Open the participant ID, contact the participant to schedule a mutually agreed date and time. During scheduling, be sure to confirm their address and telephone number for upcoming appointment. The Schedule Generator should be used to find the participant and generate a schedule of upcoming visits at specific time points, which can be tracked on the calendar (this can only be used in the web version).

#### Visits

Before Visit

Before leaving office, identify the participant ID and download onto the mobile application. Before heading to the visit, be sure IPAD is completely charged.

• After Visit

Within **1 day** of completing visit, complete either the "Checklist Prenatal Home Visit" or "Checklist Early Post-Partum Home Visit" or "Checklist 6-week post-partum Home Visit" within the **web version** REDCap system. Click on the Participant ID, find specific Checklist (Prenatal, Early Post-partum, 6 week Post-partum), scroll to the bubble (displayed gray) and click to begin completing the form based on the previous visit. Once you have reached end of form, be sure to change status of form to "Complete" and save.

Lock this record for this form? If locked, no user will be able to edit this record on this form until someone with D bock Lock/Unlock privileges unlocks it.
.ock/Unlock privileges unlocks IL
Save Record
Save and Continue
Save and go to Next

#### Following the Prenatal Visit: Participant Interactions/ Call Log

After the Prenatal home/clinic visit, contact mother's **bi-weekly** to answer questions, provide additional education and support with breastfeeding and their healthy lifestyle goals set. Any **contact** (phone call, text message, home/ clinic visit) made with mother and topics discussed should be documented in the form "Participant Interaction". Once you have reached end of form, be sure to change the status of form to "**Complete**" and **save**.

# \*During any contact, if the mother has delivered her infant. Please complete the form "Baby Data".

#### Following the Early Postpartum Visit: Participant Interactions/ Call Log

Following the **Early Postpartum Visit** and breastfeeding is established; Interventionist's will make **monthly** calls and track in RedCap. Any **contact** (phone call, text message, home/ clinic visit) made with mother and topics discussed should be documented in the subsequent form "Participant Interaction". Once you have reached end of form, be sure to change status of form to "**Complete**" and **save**.

\*If using the IPAD, while collecting information and In the case of an emergency where information collected has not been synced, such as IPAD turning off because of low battery, use the "Send Emergency Data Dump" that appears at the bottom of the REDCap mobile application, which will send all data collected to the full server.

\*Any time a change is made or something new is documented, make sure it is saved.

#### Form Completion Tracking

As information is collected in REDCap, keep track of the completion of those forms by switching the "status" of the form being complete. This can also be used to guide work flow of upcoming events and scheduling participant home visits.

- Incomplete= not complete
- Unverified= complete, but needs review by Project Manager
- Complete= After verified by Project Manager

15	10.00.7	i de la compañía de l	2,22,02	530.05	C. C	191.012.01	Marine.	19/10/20	0220343	C. C. State	2.688	Sec. 11	alisyle	1772 12	Statistic.	Sec. 1	2012	22.2475
1.	1.00	49.94		9)10101010101010101010100	r sta	1.000	$ f_{\rm M}$		1.1			100					13.9F	
E	530 L	eae	enc	i toi	r sta	itus	ICC	ons	-935	100.00					220			1. A.S.
腔	1.1.1		2016-055	Sec.	1000000	den var	Ng baard	Sec.Les.19	- 16 M S	1.1	$c \leq 1$						1.20	
	1236	1993	224			·	Sec. 24		12.00				(init)	278	(2022) 1		1277-14	9.256
R	14	1	elaany,e		lete	1 3.00	1		10	- SZCE	1		-	1. 104.0	95244	11	2	2362
1.		- 1. II.		nub	iere	1. 1.	SH IC	UII.	ihie	ie i	(110	ua	la	54	vec	1   後	۲.	1253
1			1. 1. 1. 1		119 19 9 11		33520	2233	lation (						3 N 13	$f^{-1}$	200	6492 (
12	1	1.725	10.25	Patient Andrews Record			1997	20.822		22.72.52				1.	6.600		200	
13	14		Inv	erifi	00				20 A.F		3974					388 S		14.14
臣		A ANTALA	Sec.	 					1999 B	i Stalini	6.25%		262.0	1994			1964	Sec.
1			2012		Service -		144.66		12640				経営的	10.62	10.23			
13	11	1 14	1996-07	nple	1.1.1.1.1.1.1	417-12-1	6.2.2.2	1.1.7	126.02		Ul est	20.4			(Aless	SSIL		
13	65 L	1	JOL	npie	le	1.1 1.1	1000	1.44	1000		220751							1
12	200	12441	di takin	ska statege	letter (	1.14	199.77	$(g_{1}, g_{2}) \in \mathbb{R}^{n}$				2.19			复建的	12:00	Stigent.	
18	1.1.1.1.1.1.1	1.1.1.1.1.1.1.1.1	121, 121, 12	Conterner .		1.00.000			1 Carry		10.00	2007268	26.22.27.1	200.00				

#### Overview: Collecting data using the REDCap Mobile App

- 1. OFFLINE: **Collect data** from participants using the Mobile App offline.
- 2. ONLINE: Send collected data back to the REDCap server.
- 3. ONLINE: Refresh the project on the Mobile App.

#### Detail: Send collected data back to the REDCap server

When you return to an online environment (e.g. back in your office with WiFi), you can send the data you collected on your mobile device to the Main REDCap project. This will add the data collected on the mobile device to the main REDCap project. If record names or data values conflict, you will be given the opportunity to make adjustments before completing the upload.

- 1. ONLINE: Data for newly created subjects are sent to the REDCap server. The data are sent, and the new subjects and data are added to the **REDCap Study project.**
- 2. ONLINE: When data has been collected for aiready existing subjects, new data values (on the mobile device) are compared with the preexisting data values found (on the REDCap server). If the newly collected values are different from the pre-exisitng values, the Mobile App will ask whether or not you want to overwrite the old data (on the server) with the new data (being sent from the Mobile App).

**RC New Features** 

Are you atuck? Sond Emergency Data Dump **Confirm Changes Made to Existing Records** Mobile changed; server unchanged

> Mobile Value **Q** 2015-08-25

O 2015-08-25

C Unverified

Mobile changed; server also changed

[figure not shown]
Key:

Send the data to the server? OYes ONo Hide details

Server Value

(no file)

() Incomplete

3.

tana.

ONLINE: After sending the Mobile App data to the REDCap server, the Mobile App will prompt you to refresh the project.

RC\_APP\_2016-08-25\_100519\_950204.png (10.2 KB)

11/30/2017 Revised

Record u0002 - Mobile changed

be sent by tapping it. Event Field Name

[figure not shown]
pasaline Signature

taseine Complete?

une Date of Dirth Islasting Birth Date Standard

#### Detail: Refresh the Project on the Mobile App

It is recommended to click "Clean & Reset Mobile Project" to remove all data stored on the mobile device and replace with the most current project information from the main REDCap project.

#### What is "Send Emergency Data Dump"

When something prevents the app from sending data back to the server normally, you can use "Send Emergency Data Dump" option to send data to the server as a csv file. The file will show up under Mobile App File Archive tab.

	Send Emergency Data Dump
data is so im be parsed m function prop	's data to the server might rarely fail due to software limitations. Because the portant, this alternate mechanism sends data to the server as a CSV that can anually. It should only be used in emergencies, and it requires the Internet to berly. The CSV file will show up under the REDCap Mobile App icon on the left- and under the Mobile App File Archive tab.

# Aminity Check list We're Prepared!

4000

Learn best practices. Decide what you want. Tell your care team your wishes. Being prepared helps you and your new baby have a great hospital stay.

My Name	Source	Henry	Ford Hospital Detro	it
			(Where I received the checklist.)	
	My Champion(s):		POSTPARTUM APPOINT	MENTS
	My Doctor/Midwife:		DATE / TIME	AM PM
Build	My Baby's Doctor:		DATE / TIME	AM PM
My Team	My WIC: N/A		DATE / TIME	AM PM
	My Home Visitor: N/A		DATE / TIME	AM PM
	Other:	[	DATE / TIME	AM PM
REFERENCE	PRACTICES	OFFERS	I'M PREPARED & WANT	I RECEIVED
DI-	Wait At Least 39 Weeks			
Plan	Comfort During Labor			
	Skin To Skin Right After Birth			
Fall	Delayed Routine Procedures	$\mathbf{V}$		
In Love	Magical First Hour Without Interruptions	V		
	Help With Baby's First Feed	$\checkmark$		
Nourish	Help Learning How to Breastfeed			
NUUIISII	Help Learning How to Hand Express Milk	$\checkmark$		······
	Keep My Baby In The Room With Me			
Keep Baby Close	Continued Skin to Skin	$\mathbf{V}$		
Bubyolose	My Quiet Hours: FROM AM то AM	V		
Learn	Feed My Baby on Cue			
Your Baby	Comforting My Baby	$\checkmark$		
Protect	No Pacifiers or Bottles	$\checkmark$		
FIOLECT	No Formula (Unless Medically Necessary)	$\mathbf{V}$		

#### MOTHERS: Consider sharing this with your care team, including WIC.

Baby's Name:						
Birthdate:				Age:		 
Birth Weight:	÷	Length:		Head	Circ	
Discharge Date:	/	/	Weig	ht:		 

At Discharge Baby Has Been:	🗌 Breastfed	🗌 Formula Fed	Combination
Notes:			
Mom's Postpartum HCT/HG:		We	ight:

# Stay Connected with Local Resources

#### Your Detroit Health Department

Together Toward a Healthier Detroit

The Detroit Health Department wants to make Detroit a city where all babies have an opportunity to be healthy and well. We are here to link you and your family to information, services and community resources, and to share important information for your and your baby's health.

MY BABY helps you remember six important health facts:

 $\pmb{M}$  ake it to Your Due Date: Your care team is there to help you carry your pregnancy full term.

Your Medical Home: Make sure you have a primary care doctor.

**B**aby's Medical Home: Find a pediatrician for your baby by your third trimester of pregnancy.

 $\pmb{A}\text{BC'S}$  of Safe Sleep: Remember to put your baby to sleep Alone, on her or his Back, in a Crib – and do not Smoke.

Breastfeeding: Mommy's milk is best - breastfeed!

 $\pmb{Y} \text{our Choice: Plan 18 months between pregnancies for your and your baby's good health.$ 

#### Health Department Services for Moms, Babies & Families

- · Women, Infants and Children (WIC) Nutrition Program
- Immunizations
- · Lead screening and case management
- · Vision and hearing screening
- Children's Special Health Care Services
- [name] Maternal Child Health Referral Hotline
- Safe sleep education
- · Car seat safety education

### User\_WATT Mobile Download Instruction

To quickly access WATT on your mobile device (smartphone, tablet, etc.), follow the steps below to create an icon on the home screen of your device.

#### **Apple iOS Devices**

- 1. Open your internet browser and visit your program or project site. Once on the site, click on the site's menu icon and go to the "Login" page.
- 2. Click the "Download" button on the menu of your browser.
- 3. Select "Add to Home Screen" from the list of download and saving options.
- 4. Click "Add" to save the icon to your device's home screen.

#### **Android Devices**

- 1. Open your internet browser and visit your program or project site. Once on the site, click on the site's menu icon and go to the "Login" page.
- 2. Click the "Bookmark" button on the top menu of your internet browser.
- 3. Select "Add Bookmark" from the list of download and saving options.
- 4. Select the "Home Screen" folder to save the icon to your device's home screen.

#### Additional resources and training materials are available, such as:

- The "Diet for a Healthy Breastfeeding Mom" powerpoint (slides shown on the next page)
- The "Orientation Handbook for Peer Counselors" purple binders (see binder cover below)

Mothers Allied with Mothers Around Breastfeeding Encouragement And Renewed Health

# MAMA BEAR Orientation Handbook for Peer Counselors

## Diet for a Healthy Breastfeeding Mom

raining CHW. 11.23.

Tips and suggestions for reference when working with Breastfeeding Mothers in MAMA Bear Study Presented by: [name] MS. CLS. PHP

#### Eat a well-balanced diet for your health

- Breast milk can meet baby's nutritional needs even when not eating perfectly.
- Baby won't be harmed by occasional dietary lapses doesn't mean that MOM won't suffer.
- Body draws on its reserves, which can eventually become depleted.
- Encourage: Eating small meals with healthy snacks in between the way she may have done during pregnancy –good way to keep your hunger in check and energy level high.

Don't count calories & Aim for slow and steady weight loss

- Most women who are breastfeeding need about 500 calories more than moms who aren't – that's a total of 2,000 to 2,500 calories per day.
- Encourage mom to follow hunger as a guide to how much need to eat.
- Encourage mom to lose weight gradually and plan to return to prepregnancy weight within 1 yr.
- Most women can safely lose a pound each week by combining a healthy diet with moderate exercise.
- Large drop in calorie intake can affect milk supply, discourage going on a crash diet to lose weight quickly.

Include a variety of health foods &

**Choose Good Fats** 

Encourage eating a mix of carbohydrates protein, and fat at meals keeps you feeling full longer and supplies the nutrients your body needs.

- Encourage consumption of Complex carbs like whole grains and cereals
- Fresh fruits and vegetables not only provide more nutrition than processed starches and sugars, they provide longer-lasting energy
- Limit saturated fats and avoid trans fats, both of which are considered unhealthy

#### Take extra steps to avoid contaminants

- Minimize:
  - Pesticides
  - Insecticides
  - other chemicals that you ingest can make their way into your breast milk.

[figure not shown]
#### Go easy on the alcohol

☐ If mom decides to consume an alcoholic drink; encourage her to either breastfeed her baby or express her milk first and store it for later.

After consumption of alcohol; encourage her to wait at least two hours before breastfeeding her baby or she may need to "pump and dump."

#### Drink plenty of water and limit caffeine

[figure not shown]
- Good guideline to follow is drink to satisfy thirst
- Most experts suggest that nursing moms limit their consumption of caffeine (including coffee, tea, soft drinks, energy drinks, chocolate, and coffee ice cream) to no more than 300 mg per day. That's about as much as you'd get in three 5ounce cups of coffee. You may want to drink even less if you're nursing a newborn or preterm baby

A supplement doesn't take the place of a well-balanced diet, but it can provide some extra insurance on those days when taking care of the new baby especially if it keeps mom from eating as well as she'd like

#### Additional Resources

- https://www.womenshealth.gov/breastfeeding/index.html?from=AtoZ
- https://www.womenshealth.gov/itsonlynatural/
- https://www.womenshealth.gov/files/assets/docs/breastfeeding/itsonlvnatural/breas tfeedingguide-africanamerican-english.pdf
- USDA- Choose MyPlate
- https://www.choosemyplate.gov/ten-tips
- Exercise Guide for Post-partum mothers
- http://makeyourbodywork.com/postpartum-exercise-guide/

#### Analysis Plan:

**Aim 1: Feasibility of recruitment and retention:** Feasibility will be assessed at multiple points: enrollment rate (percent of eligible and approached women); percent of participants for whom study staff is notified of hospital admission for birth; percent of participants completing each additional data collection point. By compartmentalizing our feasibility assessment in this R21 exploratory/developmental project, we will be better able to target specific areas for refinement to inform our planned phase III trial. Retention will be assessed by the percent of participants who complete the 20 week postpartum data collection visit.

**Aim 2:** Acceptability will be measured at each data collection point using a brief questionnaire developed by the research team that will allow participants to rate the value and utility of the intervention content and give their opinions about the format, ease of use, and delivery method. Control group participants will be asked a similar set of questions to compare satisfaction with usual care practices. Engagement will be assessed as percent of intervention arm participants completing each planned intervention contact and by the frequency of log-ins to the online system, use of web/mobile-based tracking tools, and interactions with peer counselors. Feasibility and acceptability will be assessed separately from, but also in relation to the primary outcomes of breastfeeding duration and weight retention. For example, we will assess the number of women who discontinue BFing but continue tracking diet and exercise. These results will guide our structured interview questions planned for the final data collection visit (20 wks postpartum).

Aim 3: Estimate the preliminary effect size of the intervention relative to a) the control group (at 20 weeks postpartum) and secondarily to b) patients in the same health system who are not enrolled in our study (via electronic medical records at 6 weeks postpartum) on: (1) breastfeeding duration, and (2) postpartum weight retention. Statistical Analyses: Subjects will be randomized to treatment (TRT) or control (CNT). Adequacy of the randomization: Randomization adequacy will be tested by comparing relevant baseline maternal and infant characteristics between the two study arms. Where substantive differences exist, they will be controlled for in subsequent analyses. We will test the degree of similarity, however, following Altman we will be guided by the degree of dissimilarity, not strict statistical significance. Outcomes and Analysis: The data on *n* participants are denoted by with outcome and explanatory variables in the *i*-th participant. The two main outcomes are: (1) Duration of breastfeeding assessed by number of days postpartum at infant weaning (possible range=0-140 d), and (2) Weight retention assessed by the ratio of the maternal weight at 20 weeks postpartum to the pre-pregnancy weight. Both outcomes are regarded as continuous and will be analyzed using linear models. If data are found to be skewed, a logarithmic or square-root transformation q will be applied to . To assess the effect of treatment on outcome we will fit the model and test the hypothesis where is the coefficient for the TRT group indicator, with CNT as referent. Results will be presented as (1) a point estimate and 95% confidence interval for, with and without regression-adjustment and (2) a standard two-sample t-test of  $_{\circ}H$ . Statistical Power: With a total sample size of 80 women randomized to TNT, CNT we can detect at least a moderate effect size of 0.65 (i.e., in units of standard deviation) with power of 80% (2sided test, alpha=0.05). Our objective, however, is the estimation of effect size rather than testing for significance.

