## 10/9/2017

## Mama Bear Incentive Plan for Participants in Both Study Arms (Intervention and Usual Care)

- 1. Enrollment: \$20 gift card + Mama Bear water bottle
- 2. Phone Survey: \$30 gift card
- 3. Soon after baby is born: Baby Bear board book (or notebook customized with Mama Bear logo)
- 4. ~6 week (4-8 week) postpartum clinic visit: \$50 gift card
- 5. ~20 week postpartum clinic or home visit: \$50 gift card

Additional Incentives for the Intervention Participants

- 1. Diapers and wipes (at early postpartum visit)
- 2. Bathroom scale (at 6 week postpartum visit)
- 3. Small "prizes" for using the online platform

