## **Clinic Visits**

~6-week post-partum data collection should occur at the clinic visit. This visit may occur for the participant anywhere between 2-8 wks post-partum.

After the participants' baby is born, contact the participant reminding them to schedule their post-partum visit at the clinic with the nurses. Ask the participant if the time scheduled would also be convenient for data-collection following the appointment. Document contact made within the "Contact log" on REDCap with details listed above. After the participants appointment has been scheduled, call participant 24hrs prior to their appointment providing them with a reminder of the appointment and that you will also meet with them during that visit.

If for some reason data collection cannot occur during the clinic visit, document the reason within the contact log and PLAN for completing visit. The next option for completing the visit would be over the phone and last option would be going to the participants home.

**Possible reasons may include:** No data collector available during clinic appointment, time was inconvenient for participant, or missed appointment.

[figure not shown]

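### Breastfeeding duration has no analysis rule for women lost while still feeding, and the optional log is undefined at 0 days

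*Combined protocol and SAP*

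**What the plan says.** The Analysis Plan (Aim 3, Outcomes and Analysis) defines the first main outcome as "Duration of breastfeeding assessed by number of days postpartum at infant weaning (possible range=0-140 d". It then says: "Both outcomes are regarded as continuous and will be analyzed using linear models". Results are an estimate with 95% confidence interval, with and without adjustment, and a two-sample t-test. On transformation it says: "If data are found to be skewed, a logarithmic or square-root transformation" will be used. The Statistical Power text adds: "Our objective, however, is the estimation of effect size rather than testing for significance".

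Incomplete follow-up is foreseen. Under Aim 1, "Retention will be assessed by the percent of participants who complete the 20 week postpartum data collection visit". The forms table in the Data Collector Protocol lists the Breastfeeding Intensity form only at about 6 weeks and at 20 weeks. Of the 6-week visit, the Clinic Visits section says: "This visit may occur for the participant anywhere between 2-8 wks post-partum". The Incentive Plan gives 4-8 weeks instead. The Visits Report FAQ mentions a 2-week visit as an example, but the forms table lists nothing for it.

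Some provisions limit loss. For a missed 6-week clinic visit, "The next option for completing the visit would be over the phone and last option would be going to the participants home". The Incentive Plan allows a "20 week postpartum clinic or home visit". These are data-collection steps and do not say how a missing weaning day is analysed. The documents contain no censoring rule, missing-data method or sensitivity analysis for duration.

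**The concern.** A linear model and t-test need one number per woman. The 140-day cap implies, without saying so, that a woman still feeding at 20 weeks counts as 140. It does not cover a woman seen feeding at the 6-week visit and then lost. The analyst would have to choose a handling after seeing the data, and the choices give different answers when loss differs by arm. Duration is one of two main outcomes and the stated aim is estimation, so the choice bears directly on the result.

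The second gap is narrower. Zero days is inside the stated range, and the log has no value there. Leaving the zeros out would remove any effect of the intervention on starting to breastfeed. Either transformation also moves the estimate off the scale of days.

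**Working it through.** **Inputs from the plan:** range 0-140 days; 80 women; effect 0.65 SD; power 80%; two-sided alpha 0.05; last shared data collection before 20 weeks at 2-8 weeks, that is days 14-56.

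**Assumed, because the documents give none:** 40 women per arm; all loss rates; all feeding distributions.

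1. *The plan's own figure.* The noncentrality is 0.65/√(2/40) = 2.91 on 78 degrees of freedom, which gives t-test power of 81.9% against the stated 80%. The power statement reproduces and is not at issue.

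2. *Bound for one woman.* Taking the last known day as weaning lowers her arm's mean by up to (140 − 56)/40 = 2.1 days if she was last seen on day 56, or (140 − 14)/40 = 3.15 days if on day 14. A woman with no postpartum data can move the mean by up to 140/40 = 3.5 days.

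3. *Simulation, loss unrelated to weaning within arm.* Weibull durations (shape 0.9) with a point mass at 0, capped at 140; 1,000,000 women per arm. Never starting is 20% in control and 10% in intervention; scale is 65 and 95 days. Last contact is uniform over days 14-56. The true difference is 18.9 days.

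| Loss, control/intervention | Drop women lost while feeding | Last known day as weaning | 20-week completers only | Kaplan-Meier restricted mean |
|---|---|---|---|---|
| 20%/20% | 18.5 | 16.1 | 18.9 | 18.9 |
| 25%/10% | 22.2 | 21.3 | 18.8-19.0 | 18.9 |
| 10%/25% | 14.8 | 11.5 | 18.8-18.9 | 18.9 |

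Under unequal loss, dropping is off by 22.2 − 18.9 = +3.3 and 14.8 − 18.9 = −4.1 days. The last known day is off by +2.4 and −7.4 days. With no true effect (15% never start, scale 80 in both arms), dropping gives about ±4 days, the last known day about ±5, and the other two about 0.

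4. *Loss higher in women already weaned at last contact (assumed odds ratio 3).* A 25% loss among feeding women has odds 1/3; three times that is 1, or 50% among weaned women. A 10% loss has odds 1/9; three times that is 1/3, or 25%. Completers-only then gives 14.7 under 25%/10% and 23.2 under 10%/25%, errors of −4.2 and +4.3 days. With no true effect it gives −4.4 and +4.4. Kaplan-Meier stays at 18.8-19.0, because it keeps the known weaning days.

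5. *Loss related to weaning after last contact (odds ratio 3 for weaning before day 140, last contact on day 42).* For the three loss patterns in table order, Kaplan-Meier gives 19.5, 18.4 and 20.4; dropping gives 18.8, 21.8 and 15.7. Kaplan-Meier is now also off. Dropping is closer under equal loss and Kaplan-Meier under unequal loss.

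6. *Size against sampling error.* The SD of capped days is 48-53, so 4-5 days is about 0.08-0.10 SD; the worst case is 7.4/48 = 0.15 SD. At 40 per arm the SD of the Kaplan-Meier difference is 11.3-11.8, so the 95% half-width is 1.96 × 11.3 = 22.1 to 1.96 × 11.8 = 23.1 days. Root mean squared error is similar for dropping, last known day and Kaplan-Meier (10.7-12.6). The gain is in bias, not precision.

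7. *Transformation.* The log is undefined at 0; the square root of 0 is 0. Standardised effects in assumed examples:

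| Effect acts on | Raw | Square root | Log without zeros | Log(y+1) |
|---|---|---|---|---|
| Starting only (20% vs 10% never start, scale 80) | 0.13 | 0.18 | 0.00 | 0.22 |
| Duration only (15% never start, scale 65 vs 95) | 0.24 | 0.20 | 0.23 | 0.14 |

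Pooled skewness is 0.54-0.57 raw, about −0.1 after square root and about −0.8 after log(y+1), so square root is the likelier choice in these examples.

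**The case against.** The strongest reply is that completers-only is the natural reading. Aim 3 compares the arms at 20 weeks, and the weight outcome needs a 20-week weight anyway. If loss is unrelated to weaning within arm, that analysis is unbiased even when loss is unequal. This stands. However, the plan does not specify it, it throws away known weaning days, and step 4 shows that it fails when women already weaned are lost more often and unequally by arm.

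It is also fair that this is a small exploratory study, that the bias is well below sampling error, and that every loss rate here is assumed. Those points limit severity.

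A reader might infer that unequal loss is built in, because the Peer Counselors and Interventionist protocols give monthly calls to intervention women only. The documents do not establish this. Data collectors contact participants for scheduling without restriction by arm, the baseline telephone script promises further calls, and both arms receive the same payment at 20 weeks. Loss could run either way or be equal.

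On the log, the square root is an available alternative, and the formula symbols in that sentence were lost in extraction, so an offset may have been there. An offset would settle the zero but not the change of scale.

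**Conclusion.** The gap is real and of minor to moderate severity. The plan leaves the duration estimate to an unstated choice among handlings. In the assumed cases of unequal loss, that choice shifts the estimate by about 2 to 7 days, generally around 0.1 SD, against a half-width of 22-23 days. No actual size can be given, because the documents give no loss rates.

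Three stronger readings are not supported. One is that the linear model is wrong for a bounded outcome: with complete follow-up and women still feeding counted as 140, the raw mean difference is valid. Another is that the analysis fails at zero days: that needs skewed data, the log rather than the square root, and no offset. The last is that the estimate would mis-size the planned phase III trial: the Aim 1 sentence on that trial concerns feasibility, and the plan does not say that this estimate will set its size.

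**What to change.** In the Analysis Plan, Aim 3:

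1. Define the target as the difference in mean breastfeeding days to day 140, with women who never start entered as 0 and women still feeding at the 20-week visit counted as 140.
2. Keep known weaning days for all women. Censor women lost while feeding at their last feeding status from visits common to both arms, so that intervention-only calls do not add information to one side. Estimate the difference by Kaplan-Meier restricted mean to day 140 with a 95% confidence interval. When no one is lost this equals the planned raw mean difference. Pseudo-value regression is one option for the adjusted estimate.
3. Add one sensitivity analysis that sets lost women to weaned at last contact or to 140, by arm. Report women with no postpartum data by arm.
4. Remove the log and square-root option for duration. Keep it for the weight ratio, where zero does not arise.

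The cost is SAP wording and slightly more analysis work, provided the 6-week and 20-week forms record feeding status and weaning day; the form content is not shown, so that must be confirmed. An assumption about loss after last contact remains and should be stated.
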